diet, exercise, and behavior modification. There is also evidence to support the use of this efficacious program in reducing postpartum weight. Further, recent evidence suggests that longer duration of breastfeeding is associated with lowering T2DM incidence, reducing maternal postpartum weight, and resetting maternal metabolism after pregnancy. Breastfeeding also protects against breast cancer, ovarian cancer, and T2DM. Despite these findings, no studies have addressed the role of intensive breastfeeding support combined with an efficacious weight loss program to reduce postpartum weight, thereby reducing progression to T2DM after pregnancy.

The American Academy of Pediatrics and the World Health Organization recommend breastfeeding for the first 6 months of life. In Kansas,  $79\%^{73}$  of women with a BMI  $\geq 25$  start breastfeeding, and only  $29\%^{73}$  still breastfeed with some supplementation (defined as "any breastfeeding") at 6 months postpartum. The Kansas rate for high BMI women of 29% is unacceptable and an urgent public health concern when compared to the 6-month breastfeeding rate for normal BMI Kansas women of 51% and the Healthy People 2020 goal of 61%. In the proposed randomized controlled trial, we seek to determine the feasibility and efficacy of a combined breastfeeding, DPP-based program in a cohort of overweight/obese women to be followed during pregnancy through 6 months postpartum. Our trial will have three study arms: DPP plus breastfeeding (Tx1); DPP Only (Tx2); and Usual Care (Tx3). A total sample of 60 pregnant women in their 1st or 2nd trimester with a BMI  $\geq 25$  will be recruited. Eligible participants are randomly assigned to a study arm (20 per arm).

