## Section II. Research Plan and Design

#### A. Study Design Overview Figure 1. Study Design Screen individuals for eligibility After meeting study inclusion criteria, randomize individuals into Tx1, Tx2, or Tx3 Tx2 Tx3 Intervention (Tx1) **DPP** plus **DPP Only Usual Care** Breastfeeding (N=20) (N=20) (N=20) Ρ DPP - 16 sessions: Core Regular prenatal care DPP - 16 sessions: R R provided by physician curriculum (Phase I) Core curriculum (Phase I) E Е **Breastfeeding Education** N Ν 2-hour curriculum Α Α (between weeks 20 - 24) т т Breastfeeding Booster Α Α Session 1-hour curriculum L L (between weeks 28 - 32) Р At delivery – in-hospital At delivery - in-hospital At delivery - in-hospital 0 breastfeeding support breastfeeding support breastfeeding support s DPP - 15 sessions: Post-DPP - 15 sessions: Т core curriculum (Phase II) Post-core curriculum N (Phase II) Α **Breastfeeding** т Т Assessment (at five Α Α separate time points)

This is a three-arm pilot randomized controlled trial (RCT) to implement as well as determine the feasibility and efficacy of an intervention that is based on the Diabetes Prevention Program and includes intensive breastfeeding counseling and support among a cohort of overweight and obese pregnant women. Upon meeting eligibility criteria, participants will be randomly assigned to the DPP plus breastfeeding (intervention, Tx1), DPP Only (Tx2), or Usual Care (Tx3), and will be followed during pregnancy through 6 months postpartum. Participants in Tx1 will receive the DPP and targeted breastfeeding support during pregnancy through 6 months postpartum. Participants in Tx2 will receive the DPP only. Participants in

Tx3 will receive care as usual. Usual care is described as obstetrical care that women with normal BMI receive and that is provided by the same provider ([name]).

At recruitment and at study closure, participants will complete four survey instruments; each of which assesses women's knowledge of physical activity, nutrition, and breastfeeding (see appendices 1 through 4). Also, postpartum women will complete the Edinburgh Postnatal Depression Scale (EPDS, see appendix 5) and a study coordinator will assess postpartum women's breastfeeding experience with the Bristol Breastfeeding Assessment Tool (BBAT, see

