### C. Number of Participants

This IRB protocol pertains to the recruitment of eligible participants from two obstetrical clinics: one clinic at Via Christi Health (VCH), a regional hospital in Wichita, and another clinic at Kearny County Hospital, a full-service hospital in rural southwest Kansas. About 45% (16,797) of Wichita's Hispanic population is female and of reproductive age, 102 and the VCH clinic sees a high volume of this at-risk population at an average of 123 pregnant patients per month, with an average pre-pregnancy BMI of 30.5 (personal communication by senior management staff at VCH on January 18, 2017). These socio-demographic and health data are similar to those of atrisk rural pregnant women in southwest Kansas who visit Kearny County Hospital (KCH) for prenatal and postnatal care. [name], maternal fetal medicine specialist, sees pregnant women at both of these locations (VCH and KCH), and he and his staff will actively assist with patient recruitment. Our goal is to randomize a total of 72 eligible participants (24 women in each study arm, which translates to 12 women from each recruitment site). Our recruitment target of overweight or obese pregnant women will involve 50% Hispanic women (who are English-speaking) and 50% other race including non-Hispanic whites. The population of pregnant women in southwest Kansas who deliver at Kearny County Hospital, Lakin, Kansas, is estimated to be 300 individuals, of which 75% (or 225 individuals) have a BMI  $\geq$  25 and  $\leq$  35.

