6. Able to use Facebook
7. Able to use Skype, FaceTime or Zoom
Exclusion
Pregnancy complications that require emergency care
2. Thyroid disease
3. Multiple gestation
4. Substance abuse within last 3 years
5. ART (Assisted Reproductive Technology) pregnancy
6. Current smoker
7. Prior bariatric surgery
8. In weight-loss program within 3 months of conception
9. BMI ≥ 35
10. Unable to attend intervention/follow-up visits
11. Unwilling to self-monitor data collection
12. Unable to complete intervention
13. Presence of any condition that limits walking
14. Presence of any condition that limits following diet
recommendations
15. Pregnancies complicated with fetuses diagnosed with
lethal malformations/conditions

If the participant meets enrollment criteria, then the research coordinator will call her again to assign her a time and place for the orientation session, to complete study-related survey instruments, and to obtain her email address to provide her with informed consent materials for review. Participants are informed that they will earn incentives to continue and complete the study: (1) a \$50 gift card at study entry, (2) a digital scale and pedometer at delivery, and (3) a gift up to \$75 for baby at Walmart's baby registry at study closure. Investigators will issue incentives in accordance with policies set forth by

IRB (please refer to the heading titled "Self-Administered Surveys and Incentive to Participate" below for additional detail regarding participant incentives).

Our recruitment target of overweight or obese pregnant women will involve 50% Hispanic women (who are English-speaking) and 50% other race including non-Hispanic whites. We anticipate meeting our recruitment goals through multiple approaches. We will promote the study via targeted mailings and clinic posters. We will advertise and develop study materials in English only. We will recruit over a period of 9 months, planning to randomize 2-3 participants

each week, or 1-2 participants per site. Our goal is to randomize a total of 72 pregnant women (24 women in each study arm, 12 women per site). Given an attrition rate of 20%, this will leave us with 60 women total (20 women in each study arm, or 10 women per site in each study arm).

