Sample Size and Randomization. The primary outcomes of interest are: (1) postpartum weight loss; (2) HbA1c and mean arterial blood pressure; and (3) breastfeeding duration. A total of 60 participants (20 per study arm) will be recruited. The results from this pilot study will be used in sample size estimation for a future study that is sufficiently powered to detect a clinically meaningful effect size. Due to the nature of this project being a feasibility study, the sample size in the proposed study is not based on providing adequate power to detect a clinically meaningful effect size across the three study arms. Block randomization with block size of 5 participants will be employed. A sequence of 12 random integers will be generated using a computer algorithm. The first 4 integers of the sequence will be assigned to the DPP plus breastfeeding arm; the next 4 integers will be assigned to the DPP only arm; and the last 4 will be assigned to the usual care arm. Blocks will be assigned to arms in the increasing order of sequence of integers generated.

**Statistical Analysis.** For baseline data characteristics, descriptive statistics will be reported as mean and standard deviation for continuous variables and as count and percentage for categorical variables. Depending on the distribution of the continuous variables, the Kruskal-Wallis test or ANOVA will be used to test for differences in continuous variables across the three arms. Chi-

Square test of independence (or Fishers exact test if 25% of cells have counts less than 5) will be used to assess the association between categorical variables and the three arms. The analysis will be based on "intention-to-treat" principle. A two-sided alpha level of 0.05 will be used to determine statistical significance. A 95% confidence interval will also be reported.

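### The number to be randomised is given as both 72 and 60, the allocation scheme provides only 60 places, and 20% attrition from 72 leaves 57.6 rather than 60

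*Combined protocol and SAP*

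**What the plan says.** Two sections set the randomised total at 72. Section II.C states "Our goal is to randomize a total of 72 eligible participants". Section II.D repeats it, "Our goal is to randomize a total of 72 pregnant women (24 women in each study arm, 12 women per site"), and then applies a loss rate: "Given an attrition rate of 20%, this will leave us with 60 women total", which it breaks down as 20 per arm and 10 per site within each arm.

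Four other places use 60 for women who are entering the trial:

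- Section I.B, after announcing a total sample of 60: "Eligible participants are randomly assigned to a study arm (20 per arm").
- Figure 1 in Section II.A, below the randomisation step: "Breastfeeding (N=20) (N=20) (N=20").
- Section III, Sample Size and Randomization: "A total of 60 participants (20 per study arm) will be recruited".
- Section IV.A.a, which gives total enrolment as 60.

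The same paragraph of Section III sets out the allocation: "Block randomization with block size of 5 participants will be employed. A sequence of 12 random integers will be generated", and "The first 4 integers of the sequence will be assigned to the DPP plus breastfeeding arm". The other two arms get 4 integers each, and blocks are then given to arms in the order of the integers. The paragraph also says that the sample size was not chosen to give adequate power. The Missing data paragraph of Section III expects little or no missing data.

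**The concern.** The number randomised and the number left after attrition are different quantities, and the plan uses 60 for both. If 72 are randomised, the allocation scheme runs out after 60 women and nothing says how the remaining 12 are assigned. Extending the list after the fact is what a sequence fixed in advance is meant to prevent. The enrolment total in Section IV.A.a would also be exceeded by 12.

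The number enrolled is one of the pilot's own feasibility measures (Section III, Outcome Measures) and is reported every 12 months (Section IV.B.c). With two totals in the plan, a reader of those counts cannot judge whether 60 enrolled means recruitment is complete or 12 short. The plan does not say this itself; it is an inference from the two totals.

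**Working it through.** **Inputs.** 72 randomised, 24 per arm, 12 per site in each arm, 20% attrition, 60 remaining (Sections II.C and II.D). 60 in total, 20 per arm (Section I.B, Figure 1, Section III; total only in Section IV.A.a). Block size 5, 12 integers, 4 integers per arm (Section III).

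**1. Stated totals.** 72 − 60 = 12 women; 24 − 20 = 4 per arm.

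**2. Capacity of the allocation list.** The plan does not state a capacity, so it is derived here by reading each integer as one block of 5. The statement that blocks are assigned to arms supports that reading.

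- Places: 12 × 5 = 60; per arm: 4 × 5 = 20.
- Shortfall against 72: 72 − 60 = 12.
- Whole blocks needed for 24 per arm: 24 / 5 = 4.8, not a whole number. Blocks of 5 given whole to one arm cannot produce exactly 24.

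**3. The plan's attrition figure.** The plan says that 72 at 20% leaves 60.

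- Remaining = N × (1 − d): 72 × 0.80 = 57.6 in total; 24 × 0.80 = 19.2 per arm; 12 × 0.80 = 9.6 per site within arm.
- Gap: 60 − 57.6 = 2.4 women, or 0.8 per arm.
- Attrition implied by 72 falling to 60: 1 − 60/72 = 16.7%.
- Working backwards: 60 / 0.80 = 75, whereas 60 × 1.20 = 72. The stated 72 is what results from adding 20% to 60 rather than dividing 60 by 0.80.

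**4. If 60 are randomised.** The plan attaches the 20% only to 72. Assuming it also applies to 60: 60 × 0.80 = 48 completers; 20 × 0.80 = 16 per arm.

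**5. Lists that would hold 72.**

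- Block size 6 with the existing 12 integers: 12 × 6 = 72; 4 × 6 = 24 per arm.
- Block size 5 with 15 integers: 15 × 5 = 75; 5 × 5 = 25 per arm. If blocks are filled in order and randomisation stops at 72, the last block has 2 of its 5 places used, giving 25 + 25 + 22 = 72.

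**The case against.** The best defence is that 60 is the completer target: Section II.D randomises 72 and has 60 left, and that figure was then carried into the other sections. The plan nowhere says in so many words that 60 will be randomised. This may well explain how the figures arose, but it does not remove the conflict. Section I.B ties 20 per arm to random assignment, Figure 1 places it below the randomisation step, and Sections III and IV.A.a use 60 for women recruited or enrolled, all before any attrition. It does not help the allocation list either, which must hold everyone randomised.

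A second objection is that the stated 60 can be recovered by rounding. Section II.D breaks its remainder down to 10 per site in each arm; 9.6 rounds to 10, and 10 × 6 cells = 60. That is correct, and it is why the attrition point is minor. Rounding each of six cells up still overstates the expected total by 2.4 women, and rounding by arm to the nearest whole number gives 3 × 19 = 57.

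A third objection is that the 20% may be a cautious recruitment allowance, while the Missing data paragraph voices a general expectation without a rate. That is a fair reading, so this is a tension rather than a numerical contradiction. However, the paragraph names attrition as a source of missing data and permits complete-case analysis only below 5% missing, so the two expectations lead to different analyses.

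**Conclusion.** The concern holds. The randomised total is inconsistent by 12 women (4 per arm), and the allocation scheme as written supports only 60. That second point rests on reading each integer as one block of 5. The attrition arithmetic is off by 2.4 women in total and is of minor importance.

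No loss of power is claimed, since the plan does not base its sample size on power. Expected completers are 57.6 (19.2 per arm) if 72 are randomised, or 48 (16 per arm) if 60 are randomised and the 20% rate is assumed to carry over. If the expectation of almost no missing data held instead, they would be close to 72 or 60.

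**What to change.** State one governing randomised total and use it in Sections I.B, II.A (Figure 1), II.C, II.D, III and IV.A.a.

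- **If 72 governs:** restate expected completers as 57 to 58, about 19 per arm, and specify a list with at least 72 places before enrolment. Block size 6 with 12 integers gives exactly 24 per arm. Block size 5 with 15 integers gives 75 places and arms of 25, 25 and 22 when stopped at 72. Either choice settles only the count. Neither addresses whether whole blocks should go to a single arm, and neither secures 12 women per site in each arm, because Section III describes no stratification by site.
- **If 60 governs:** the list stays as it is. Correct the 72, 24 and 12 in Sections II.C and II.D, and restate expected completers as about 48 (16 per arm), saying that the 20% is assumed to apply.

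Keeping 60 completers at 20% attrition would need 75 randomised, 25 per arm. That exceeds every stated total, does not divide evenly over two sites (25 / 2 = 12.5), and is not required by any power figure in the plan.

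In either case, reconcile the 20% in Section II.D with the Missing data paragraph. If enrolment has already begun, document the governing total and any extension of the list.

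**Cost.** One amendment, which Section IV.I requires to be submitted for approval before implementation, and a slightly less favourable completer figure. If 72 governs, there is also a new allocation list and an enrolment total 12 higher in Section IV.A.a. On the assumption that only 60 were budgeted, participant compensation would rise by up to 12 × $187.50 = $2,250.

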Aim 1: Test the efficacy of Tx1 to improve 6-month postpartum weight loss among women with a BMI  $\geq$  25. The outcome of interest is 6 month postpartum weight loss measured across the three arms. Weight will be measured at delivery, and at weeks 1, 3, and 6 postpartum and at 3 months (13 weeks) and 6 months (26 weeks) postpartum. The difference in postpartum weight (weight loss) between two consecutive time points will be computed. Thus, each participant has 5 postpartum weight loss values based on weight measurements at 6 different time points. We will use the generalized estimating equation approach to compare weight loss in the DPP plus breastfeeding arm (Tx1) with weight loss in the DPP only (Tx2) and usual care (Tx3) arms, as well as weight loss between Tx2 and Tx3. The working correlation matrix will be specified after assessing the data. The model will be adjusted for the effect of age, race/ethnicity, level of education, annual household income, family history of diabetes, baseline weight, pre-diabetes status, and parity.

Aim 2: Test the efficacy of Tx1 to improve 6-month postpartum mean blood glucose (HbA1c) and mean arterial blood pressure among women with a BMI  $\geq$  25. The outcome of interest is mean blood glucose (HbA1c) and mean arterial blood pressure ((systolic blood pressure +2 (diastolic blood pressure)/3)) measured at baseline, delivery, and at 6 months postpartum across the three arms. We will use a multiple linear regression approach to compare HbA1c in Tx1 with HbA1c in Tx2 and Tx3, as well as HbA1c between Tx2 and Tx3. The model will be adjusted for the effect of age, race/ethnicity, level of education, annual household income, family history of diabetes, pre-diabetes status, parity, and baseline weight. The difference in mean blood arterial pressure at 6 months postpartum will also be assessed using a separate multiple linear regression approach after adjusting for the same covariates listed previously.

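### The plan aims for 12 women per site in each arm, but the allocation is not stratified by site and no outcome model includes site.

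*Combined protocol and SAP*

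**What the plan says.** Two sections set a target by arm and site. Section II.C states it as "24 women in each study arm, which translates to 12 women from each recruitment site". Section II.D repeats it ("24 women in each study arm, 12 women per site") and expects "20 women in each study arm, or 10 women per site in each study arm" to remain after attrition. Both present this as a goal.

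The allocation method is under Sample Size and Randomization in Section III: "Block randomization with block size of 5 participants will be employed" and "A sequence of 12 random integers will be generated using a computer algorithm". Four integers go to each arm and the blocks follow the integers, so each block of five belongs to a single arm. No stratification factor and no site-specific list is mentioned. Section IV adds only that a computer does the randomising.

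The Aim 1 model is "adjusted for the effect of age, race/ethnicity, level of education, annual household income, family history of diabetes, baseline weight, pre-diabetes status, and parity". Aim 2 lists the same eight covariates, and Aim 3 refers back to them. The models for the breastfeeding assessment, self-efficacy and physical activity scores use the same list without baseline weight. Site is in none of them, and no analysis by site is described.

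**The concern.** A target set by arm and site needs an allocation method that can meet it, and a single unstratified list cannot be relied on for that. When arms of about 20 women come from two hospitals, chance can leave them with noticeably different site mixes. Sending whole blocks of five to one arm can make this worse, because a run of women from one hospital may all land in the same arm.

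Site could plausibly matter. One hospital is a regional medical center in Wichita and the other is a rural critical access hospital. The background (Section I.B) links rural residence to lower breastfeeding rates, and breastfeeding duration is a primary outcome. Section I.F says rural pregnant women have poorer access to healthy food and fewer options for exercise, which bears on weight. In-hospital lactation support comes from the hospital itself. No listed covariate records hospital or rurality. If site does matter, an imbalance moves the arm contrast in this trial, and site variation left in the residual costs some precision. The results are also meant to inform the sample size of a later trial.

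**Working it through.** **1. The plan's own figures.** 3 arms x 2 sites x 12 = 72, and 3 x 2 x 10 = 60, so the split is internally consistent. The sequence supplies 12 x 5 = 60 assignments, which matches "A total of 60 participants (20 per study arm) will be recruited" but not 72. Section II.D says "Given an attrition rate of 20%, this will leave us with 60 women total", but 72 x 0.8 = 57.6; going from 72 to 60 is 16.7% attrition. That is a separate matter. N = 60 is used below because it is the number the described sequence can allocate.

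**2. Chance of the intended balance.** Assumption: 30 women from each site, so 10 per site per arm is the target. The enrolment order is not known, so two extremes are shown.

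- *Sites enrol in random order.* P(10/10 in all three arms) = C(20,10)^3 / C(60,30) = 5.3%. The corresponding figure for 12/12 at N = 72, under simple exchangeable allocation, is C(24,12)^3 / C(72,36) = 4.5%.
- *Each block fills from one site.* Six of the 12 blocks come from each site, and balance needs two of each in every arm: C(4,2)^3 / C(12,6) = 216/924 = 23.4%.

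**3. Size of the imbalance.** Simulation of the 12-block scheme (60,000 runs) gives:

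| | Random order | One site per block |
|---|---|---|
| SD of difference in site share, Tx1 minus Tx2 | 0.16 | 0.37 |
| P(largest and smallest arm counts from one site differ by 4 or more women) | 50% | 76% |
| P(they differ by 10 or more women) | 0.7% | 76% |
| P(some arm comes wholly from one site) | 0% | 14% |

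In the second column, any departure from balance means a gap of at least two blocks, which is 10 of 20 women; 1 - 0.234 = 76.6%.

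**4. Precision lost by omitting site.** Section I.B gives a 29% rate of any breastfeeding at 6 months for Kansas women with BMI of 25 or more, so the variance is 0.29 x 0.71 = 0.206. With the sites split 50/50, a gap g between them explains (g/2)^2 / 0.206 of it. The range for g is an assumption.

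- g = 0.10: 0.0025 / 0.206 = 1.2%, and 1/sqrt(1 - 0.012) = 1.006, so intervals are 0.6% wider.
- g = 0.30: 0.0225 / 0.206 = 10.9%, and 1/sqrt(1 - 0.109) = 1.06, so intervals are 6% wider.

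This holds on a linear scale and before the listed covariates absorb anything.

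**5. What stratification needs.** At 12 women per arm per site, blocks of five do not fit (12/5 = 2.4). With 36 women per site, 12 blocks of 3 or 6 blocks of 6 fit exactly. With 30 per site, 10 blocks of 3 or 5 blocks of 6 also fit.

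**6. Cost of the covariate.** With 60 complete cases, residual degrees of freedom in a linear model fall from 49 to 48 if race, education and income use one each, or from 43 to 42 if they use three each. The coding is an assumption.

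**The case against.** Several points on the other side are sound.

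- **The patients may be alike.** A reader might infer from the hospital types that the populations are very different. Section II.C says the opposite: it describes the socio-demographic and health data at the two sites as similar. The same maternal fetal medicine specialist sees women at both, and the DPP modules are pre-recorded and shared. The statement on rural breastfeeding is general background, not data from these clinics. The documents support a difference in setting only.
- **12 per site is a goal.** Missing it would not breach a commitment. But a goal set by arm and site still calls for a method that can reach it.
- **A chance imbalance is not bias.** A reader might infer that site imbalance adds a systematic error to the contrast. Under randomisation it is sampling error. With random enrolment order, a 10 to 30 point gap times 0.16 gives 1.6 to 4.8 points, and that is already part of the unadjusted standard error of sqrt(2 x 0.206/20) = 14.3 points, not an addition to it. It would be less fully reflected if blocks filled from one site, because a standard error computed as if women were allocated singly ignores the block assignment.
- **The gain is small.** For site to explain 5% to 15% of the variance, the gap would have to be about 20 to 35 points. Race, education and income may already carry part of any site effect.
- **The formula is for linear models.** It does not carry over to the Cox model, where adding a covariate changes the hazard ratio being estimated and need not shrink its standard error in this way.

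The pilot is not sized for power, which limits what is at stake. It still tests efficacy at a two-sided 0.05.

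**Conclusion.** The point holds as a mismatch between design and method. The plan states an arm-by-site split that its allocation scheme is unlikely to produce (5.3% to 23.4% for exact balance, assuming 30 women per site and 60 in all), and no outcome model accounts for site. The imbalance could be moderate (SD of the site-share difference 0.16) or large (0.37), depending on how enrolment from the two sites interleaves with the blocks.

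The effect on the results cannot be fixed from the documents, which give no site difference in any outcome. Under the assumed 10 to 30 point gap in breastfeeding, site explains about 1% to 11% of the variance and omitting it costs about 0.6% to 6% in interval width at most. It does not follow that the planned comparisons are biased or invalid. The case for changing the plan is that the remedy is nearly free and makes the method match the stated target.

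One limit: the text between Sections II.D and II.F was not available to this review. If it specifies a list per site, the allocation half of the point falls away and the covariate half remains.

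**What to change.** - In Section III, replace the single sequence with a separate computer-generated list for each site. Allocate women individually in permuted blocks whose size is a multiple of three (3 or 6), so that each block contains all three arms equally.
- Add site as a fixed covariate to every Aim 1 to 3 model and every survey-score model.
- If allocation has already started, leave the list as it is and pre-specify the site covariate before the analysis.

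The cost is a second list and one degree of freedom per model, in models that already carry seven or eight covariates and the arm terms. In the Cox model the hazard ratio becomes conditional on site, and the plan should say so. Stratification balances the women randomised; differential dropout can still disturb the 10 per site expected at the end, which is a further reason to keep site in the models.
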